10.3.4. Pharmacodynamic Analysis (Part B Only)

Analysis of the qEEG and ERP assessments will be performed using the PD population for the double-blind treatment period. Initial details of the analysis of the qEEG and ERP data are described in [Appendix 20](#), but will be fully defined in a PD SAP.

10.3.5. Safety Analyses (Part A and Part B)

The safety analysis will be performed using the safety population for the double-blind treatment period and for the safety follow-up period, if applicable, and will be fully defined in the SAP for each Part A and Part B of the study. The safety parameters will include AEs, clinical laboratory including potential Hy's law cases, vital signs, ECG, C-SSRS, BPRS+, and CADSS parameters. For each safety parameter, the last nonmissing safety assessment before the first dose of study intervention will be used as the baseline for all analyses of that safety parameter.

10.3.5.1. Adverse Event (Part A and Part B)

For each part of the study, A and B, an AE will be considered a TEAE if the AE began or worsened (increased in severity or became serious) on or after the date of the first dose of study medication. However, an AE that occurs more than 30 days after the last dose of study medication of each part A and B, respectively, will not be counted as a TEAE. An AE will be considered a TESAE if it is a TEAE that additionally meets any SAE criteria.

The number and percentage of participants reporting TEAEs in each study treatment will be tabulated as follows:

- By system organ class and preferred term
- By system organ class, preferred term, and severity.

An AE will be considered a TEAE if:

- The AE began on or after the date of the first dose of study treatment; or
- The AE was present before the date of the first dose of study treatment, but increased in severity or became serious on or after the date of the first dose of study treatment

If more than 1 AE is reported before the first dose of study treatment and is coded to the same preferred term, the AE with the greatest severity will be used as the benchmark for comparison with the AEs that were also coded to that preferred term and that occurred during the period. An AE that occurs more than 30 days after the last dose of study treatment will not be counted as a TEAE.

An AE will be considered a TESAE if it is a TEAE that additionally meets any SAE criteria

The number and percentage of participants reporting TEAEs in each study treatment will be tabulated as follows:

- By system organ class and preferred term
- By system organ class, preferred term, and severity.

The number and percentage of participants reporting treatment related TEAEs in each study treatment will be tabulated by system organ class and preferred term.

If more than 1 AE is coded to the same preferred term for the same participant, the participant will be counted only once for that preferred term using the most severe and most related occurrence for the summarization by severity and by relationship to study treatment.

Summary tables will be provided for participants with TESAEs and participants with TEAEs leading to discontinuation if 2 or more participants reported such events. Listings of all AEs, SAEs, and AEs leading to discontinuation by participant will be presented.

The definitions of an AE and SAE can be found in [Appendix 4](#).

10.3.5.2. Clinical Laboratory Assessments (Part A and Part B)

For Part A and Part B of the study, descriptive statistics of actual values and change from baseline for clinical laboratory values (in SI units) will be presented at each assessment timepoint by treatment. In addition, descriptive statistics for values and changes from the baseline values in conventional units at each assessment timepoint will be presented for selected clinical laboratory parameters listed in the SAP.

The criteria for PCS laboratory values will be detailed in the SAP for Part A and the SAP for Part B, respectively. The number and percentage of participants who have PCS postbaseline clinical laboratory values will be tabulated by study treatment at each assessment. The percentages will be calculated relative to the number of participants who have available non-PCS baseline values and at least 1 postbaseline assessment. The numerator will be the total number of participants with available non-PCS baseline values and at least 1 PCS postbaseline value. A supportive listing of participants with PCS postbaseline values will be provided.

10.3.5.3. Vital Signs (Part A and Part B)

For Part A and Part B of the study, descriptive statistics of actual values and change from baseline for vital signs (systolic and diastolic BP, pulse rate, weight, and temperature) will be presented at each assessment timepoint by treatment.

Vital sign values will be considered to be PCS if they meet both the observed value criterion and the change from baseline value criterion that will be detailed in the SAP for Part A and the SAP for Part B, respectively. The number and percentage of participants who have PCS postbaseline vital sign values will be tabulated by study treatment for each assessment. The percentages will be calculated relative to the number of participants who have an available baseline value and at least 1 postbaseline assessment. The numerator will be the total number of participants with at least 1 PCS postbaseline value. A supportive listing of participants with PCS postbaseline values will be provided.

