^d Height will only be measured at Visit 1 (Screening); pulse rate, blood pressure, temperature, and body weight will be assessed at every visit. Blood pressure and pulse will be assessed while the participant is supine and standing.

^e HAM-A will be assessed predose at Visits 2, 3, 4, and 6/ET. The HAM-A will be collected only from participants entering the study after the amendment has been IRB approved.

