11.3 VITAL SIGNS

Descriptive statistics of actual values and change from baseline for vital signs (systolic and diastolic blood pressures, pulse rate, weight, and temperature) will be presented at each assessment timepoint by treatment.

Vital sign values will be considered PCS if they meet both the observed-value criterion and the change-from-baseline criteria listed in [Table 11-3](#). The number and percentage of participants who have PCS postbaseline vital sign values will be tabulated by treatment group. The percentages will be calculated relative to the number of participants who have available baseline value and at least 1 postbaseline assessment. The numerator will be the total number of participants with available non-PCS baseline value and at least one PCS postbaseline value. A supportive listing of participants with PCS postbaseline values will be provided.

In addition, a tabular display showing all AEs that occurred in participants who had PCS postbaseline vital sign values will be provided.

Table 11-3 Criteria for Potentially Clinically Significant Vital Signs

Parameter	Flag	Criteria ^a	
		Observed Value	Change From Baseline
Supine systolic blood pressure, mm Hg	High	≥ 180	Increase of ≥ 20
	Low	≤ 90	Decrease of ≥ 20
Supine diastolic blood pressure, mm Hg	High	≥ 105	Increase of ≥ 15
	Low	≤ 50	Decrease of ≥ 15
Supine pulse rate, bpm	High	≥ 120	Increase of ≥ 15
	Low	≤ 50	Decrease of ≥ 15
Weight, kg	High	—	Increase of ≥ 7%
	Low	—	Decrease of ≥ 7%
Temperature, °C	High	> 38	—
	Low	< 35	—

a A postbaseline value is considered potentially clinically significant if it meets both the observed-value and the change-from-baseline criteria.

bpm = beats per minute.

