16.3 REPEATED OR UNSCHEDULED ASSESSMENTS OF SAFETY PARAMETERS

If a participant has repeated assessments before the start of the first treatment, the results from the final nonmissing assessment made prior to the start of the study treatment will be used as baseline. If end of double-blind treatment period assessments are repeated or if unscheduled visits occur during the double-blind treatment period, the last nonmissing postbaseline assessment will be used as the end of double-blind treatment period assessment for generating summary statistics. However, all postbaseline assessments will be used for PCS value determinations, and all assessments will be presented in the data listings.

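### The protocol asks for PCS counts at each assessment, but its definitions and the Part A SAP give only one any-time count per arm

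*Protocol*

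**What the plan says.** **Protocol, vital signs (10.3.5.3).** The tabulation level is stated first: "The number and percentage of participants who have PCS postbaseline vital sign values will be tabulated by study treatment for each assessment". Percentages are taken "relative to the number of participants who have an available baseline value and at least 1 postbaseline assessment", and "The numerator will be the total number of participants with at least 1 PCS postbaseline value". Neither definition refers to the assessment being tabulated.

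**Protocol, laboratory values (10.3.5.2).** The pattern is the same. The table is promised by visit, "The number and percentage of participants who have PCS postbaseline clinical laboratory values will be tabulated by study treatment at each assessment", but both definitions are any-time ones, here limited to participants whose baseline was not PCS.

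**Protocol, ECG (10.3.5.4).** This section uses the same any-time template but asks for a table by study treatment only, so there it is internally consistent.

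**Part A SAP.** Section 11.3 reads "The number and percentage of participants who have PCS postbaseline vital sign values will be tabulated by treatment group", and the by-assessment phrase is absent. It is also absent from the laboratory section, 11.2. The SAP vital-sign numerator is any-time as well: "The numerator will be the total number of participants with available non-PCS baseline value and at least one PCS postbaseline value". Section 16.3 adds that "all postbaseline assessments will be used for PCS value determinations", with no limit to the double-blind period. Section 17.0 lists no changes from the protocol.

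**Part A schedule (protocol 2.1).** For vital signs, "pulse rate, blood pressure, temperature, and body weight will be assessed at every visit". The postbaseline visits are Days 2, 8, 9, 15 and 22.

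**The concern.** A table at each assessment needs a numerator and a denominator tied to that assessment. The protocol gives neither, so a programmer must choose between repeating one cumulative figure at every visit and inventing a per-visit rule. The Part A SAP avoids the choice by not tabulating by visit, and does not record this as a departure.

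Timing matters in Part A because exposure changes by design. Participants take randomized treatment on Day 1, placebo in every arm on Days 2 to 7, and randomized treatment on Days 8 to 15. Day 22 falls a week after dosing ends. The nonclinical cardiovascular observation in protocol section 3 is a transient fall in blood pressure in dogs. One any-time count cannot place a PCS reading within this sequence, and it counts an off-drug reading in the same way as one taken during treatment.

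**Working it through.** The documents state no PCS rate, so there is no plan figure to reproduce. The check sets the texts side by side and then illustrates what a single count hides.

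**1. Texts compared**

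| | Tabulated by | Numerator and denominator |
|---|---|---|
| Protocol 10.3.5.2, laboratory | treatment, at each assessment | any-time |
| Protocol 10.3.5.3, vital signs | treatment, for each assessment | any-time |
| Protocol 10.3.5.4, ECG | treatment | any-time |
| SAP 11.2 and 11.3 | treatment group | any-time |

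Only the two protocol sections that promise a by-assessment table conflict with their own definitions. The SAP is consistent in tabulation level but does not deliver that table.

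**2. Where the merging has an effect**

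- Part A vital signs have five scheduled postbaseline readings (Days 2, 8, 9, 15, 22).
- Part A laboratory tests have one scheduled postbaseline draw (Visit 6/ET), so a by-visit table would add little.
- Part B has its own SAP, which is not among these documents. Only the protocol wording can be judged.

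**3. Size of the any-time count (assumed rates)**

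Let p be the PCS chance per reading. If the same participants are PCS at every visit, the any-time proportion is p. If visits are independent, it is 1 − (1 − p)^5, or 1 − (1 − p)^4 without Day 22.

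| p | Five readings, independent | Without Day 22 | Participants of 25 (p to independent) |
|---|---|---|---|
| 1% | 4.9% | 3.9% | 0.25 to 1.2 |
| 2% | 9.6% | 7.8% | 0.5 to 2.4 |
| 5% | 22.6% | 18.5% | 1.25 to 5.7 |

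**4. Loss of timing**

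Assume a 2% background, independent visits, and an excess on drug at the stated visits only. Placebo is 1 − 0.98^5 = 9.6% throughout.

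- 10% at Day 2 only: 1 − 0.90 × 0.98^4 = 17.0%.
- 10% at Day 22 only (off drug): the same expression, 17.0%.
- 6% at Days 9 and 15: 1 − 0.98^3 × 0.94^2 = 16.8%.

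All three are about 4.2 of 25 participants. The single count cannot tell them apart. A by-visit table would show 10% v 2% at Day 2, 10% v 2% at Day 22, or 6% v 2% at two visits.

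**5. Does pooling weaken detection?**

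This uses the difference divided by its unpooled standard error, with 25 per arm.

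- 6% at Days 9 and 15. Per visit: 0.04 / √[(0.06 × 0.94 + 0.02 × 0.98)/25] = 0.04/0.0551 = 0.73. Pooled: 0.0723 / √[(0.168 × 0.832 + 0.096 × 0.904)/25] = 0.0723/0.0953 = 0.76. The ratio falls from 3 to 1.75, but the absolute difference rises from 4 to 7.2 points.
- 10% at Day 2 only. Per visit: 0.08/0.0662 = 1.21. Pooled: 0.0738/0.0955 = 0.77. The ratio falls from 5.0 to 1.8.

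The answer depends on the assumed pattern, and the documents give nothing from which to choose one.

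**The case against.** **The wording may mean each parameter.** In 10.3.5.3 visits are called assessment timepoints, so the PCS phrase could mean each vital sign. SAP 11.3 would then implement the protocol, and 17.0 would be right for vital signs. This is possible, but the laboratory section's parallel phrase is hard to read that way, and the ECG section omits it. The ambiguity itself needs removing.

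**Timing is not lost altogether.** SAP 11.3 keeps by-visit descriptive statistics and change from baseline, a listing of PCS participants and a display of their adverse events. SAP 11.1 summarizes treatment-emergent events weekly. This stands: with about 25 per arm, timing can be recovered case by case. What is missing is a planned PCS rate by arm and visit.

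**The table may be specified elsewhere.** SAP 4.0 places table specifications in a separate document, so omission from 11.3 does not prove that the table will not be produced. This also stands, but the SAP text should still agree with the protocol.

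**Stronger readings.** A reader might infer that pooling dilutes a drug signal, because the ratios fall. The documents do not support this: the rates are assumed, and in one of the two patterns above the standardized difference is essentially unchanged. A reader might also infer that by-visit rows would cleanly separate on-drug from off-drug readings. They would not: protocol 4.1 labels Day 9 as single dose, and the timing of Day 8 vital signs relative to that day's clinic dose is not stated. Finally, a Part B laboratory value that is PCS at Day 7 in 3 of 40 participants might seem bound to reappear as 7.5% at Days 14 and 21. That follows only from the most literal reading of a section that protocol 10.3 calls a summary, and the Part B SAP may settle it.

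**Conclusion.** The inconsistency is real and the severity is minor. The protocol's any-time definitions cannot produce the by-assessment table it calls for, and the Part A SAP omits that table without declaring it. The practical consequence is confined to the Part A vital-sign PCS incidence table, which gives no rate by arm and visit and merges treatment with follow-up readings. The loss is of timing and dosing-phase attribution; a loss of detection is not shown.

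This rests on reading the phrase as referring to visits and on SAP 16.3 bringing Day 22 into the count, since SAP 11.3 names no period. The percentages are illustrations from assumed rates. The study is unpowered, and no efficacy analysis is affected.

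**What to change.** In protocol 10.3.5.2 and 10.3.5.3 and SAP 11.2 and 11.3:

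- **By-assessment rows.** The numerator is participants meeting the stated baseline condition whose value at that visit is PCS. The denominator is participants meeting the same baseline condition who have a value at that visit. Assign visits by SAP Table 16-1, including its rule of using the last nonmissing value in a window.
- **Any-time row.** Keep the existing any-time definition, using all readings as in 16.3, as a separate row shown once for double-blind treatment and once for safety follow-up.
- **Alternatively,** if the sponsor does not want the by-assessment table, declare its removal in SAP 17.0 and align the protocol wording.

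The same edit should align the baseline condition in SAP 11.3, where the numerator requires a non-PCS baseline and the denominator does not. It should also restore the word PCS to the SAP 11.2 numerator, which as printed equals its denominator.

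The cost is revised wording and one extra descriptive layout, with no new data. The downside is small counts per visit: with about 25 per arm, one participant is 1/25 = 4 percentage points, so the rows should be read as description.

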10.3.5.4. Electrocardiograms (Part A and Part B)

For Part A and Part B of the study, descriptive statistics of actual values and change from baseline for ECG parameters (ie, heart rate, PR interval, QRS interval, QT interval, and QTc interval) will be presented at each assessment timepoint by treatment.

The number and percentage of participants with PCS postbaseline values will be tabulated by study treatment. The criteria for PCS ECG values will be detailed in the SAP for Part A and the SAP for Part B, respectively. The percentages will be calculated relative to the number of participants with an available non-PCS baseline value and at least one postbaseline assessment. The numerator will be the total number of participants with an available non-PCS baseline value and at least one PCS postbaseline ECG value. A supportive listing of participants with PCS postbaseline values will be provided and will include the participant number and the baseline and postbaseline values. A listing of all AEs for participants with PCS ECG values will also be provided.

A shift table from baseline to the end of study in the investigator's overall interpretation of the ECG will be presented by treatment group for the following categories: normal; abnormal, not clinically significant; abnormal, clinically significant. A tabular display of participants with postbaseline clinically significant ECG abnormalities according to the investigator's overall interpretation will be provided.

The number and percentage of participants with a change from baseline QTc > 30 msec but not exceeding 60 msec and of participants with an increase > 60 msec will be tabulated by treatment group. A supportive listing that includes the participant identification number, all QTc values (including change from baseline values), and all AEs will be provided for all participants who have postbaseline QTc changes > 30 msec.

10.3.5.5. Other Safety Parameters (Part A and Part B)

Other safety parameters for Part A and Part B include the BPRS+, CADSS, and C-SSRS.

Descriptive statistics of actual values and change from baseline for BPRS+ total score will be presented at each assessment timepoint by treatment.

Descriptive statistics of actual values and change from baseline for CADSS total score will be presented at each assessment timepoint by treatment. The CADSS total score is defined as the sum of scores for 23 subjective items.

The number and percentage of participants with suicidal ideation or suicidal behavior as recorded on the C-SSRS will be summarized by treatment. The distribution of responses for most severe suicidal ideation and most severe suicidal behavior during the participant's lifetime, during the double-blind treatment period, and during the safety follow-up period will also be presented by treatment. Supportive listings will be provided and will include the participant number, lifetime history, and postbaseline values. Intensity of suicidal ideation, suicidal behavior type, and lethality of suicidal behavior will also be included in these listings. A listing of all AEs occurring in participants who have suicidal ideation or suicidal behavior will also be provided.

12.1. Appendix 1: Abbreviations and Trademarks

ADT	antidepressant therapy
AE	adverse event
ALT	alanine aminotransferase
AESI	adverse event of special interest
ASI	alpha slow wave index
ASSR	Auditory Steady-State Response
AST	aspartate aminotransferase
AUC	area under the concentration-time curve
BID	twice daily
BMI	body mass index
BPRS+	Brief Psychiatric Rating Scale - Positive Symptoms Subscale
CADSS	Clinician Administered Dissociative States Scale
CFR	Code of Federal Regulations
CGI-S	Clinical Global Impressions-Severity
CIOMS	Council for International Organizations of Medical Sciences
C _{max}	maximum concentration
CNS	central nervous system
CONSORT	Consolidated Standards of Reporting Trials
CSF	cerebrospinal fluid
C-SSRS	Columbia–Suicide Severity Rating Scale
CWT	continuous wavelet transform
DALY	disability adjusted life years
DSM-5	Diagnostic and Statistical Manual of Mental Disorders , 5th Edition
ECT	electroconvulsive therapy
ECG	electrocardiogram, electrocardiographic
eCRF	electronic case report form
EEG	electroencephalography
EOG	electro-oculograms
ERP	event related potential
ERSP	event-related spectral perturbation
ET	early termination
FDA	Food and Drug Administration
FSH	follicle stimulating hormone
GCP	good clinical practice
HAM-A	Hamilton Anxiety Rating Scale

HbA1c	Hemoglobin A1c
β -hCG	β -human chorionic gonadotropin
HCV	hepatitis-C virus
HIPAA	Health Insurance Portability and Accountability Act of 1996
HIV	human immunodeficiency virus
HRT	hormonal replacement therapy
HVLT-R	Hopkins Verbal Learning Test-Revised
IB	Investigator's Brochure
ICF	informed consent form
ICH	International Council for Harmonisation of Technical Requirements for Registration of Pharmaceuticals for Human Use
IEC	independent ethics committee
IP	investigational product
IRB	Institutional Review Board
ITPC	inter-trial phase coherence
ITT	Intent-to-Treat
IWRS	Interactive Web Response System
KSS	Karolinska Sleepiness Scale
LOCF	last observation carried forward
LTP	long-term potentiation
MADRS	Montgomery- Åsberg Depression Rating Scale
MDD	major depressive disorder
MI	multiple imputation
mITT	modified intent-to-treat
MMN	mismatch negativity
MMRM	mixed-effect model for repeated measures
MNAR	missing not at random
NMDA	N-methyl-D-aspartate
NMDAR	N-methyl-D-aspartate receptor
NOAEL	no-observed-adverse-effect level
OC	observed case
PCS	potentially clinically significant
PD	pharmacodynamic(s)
PI	principal investigator
PK	pharmacokinetic(s)
qEEG	quantitative electroencephalography
QTc	QT interval corrected for heart rate
QTcB	QT interval corrected for heart rate using the Bazett formula ($QTcB = QT/[RR]^{2/3}$)
QTcF	QT interval corrected for heart rate using the Fridericia formula ($QTcF = QT/[RR]^{3/2}$)
RMS	root means square

SAE	serious adverse event
3-SAOT	3-stimulus auditory oddball task
SAP	Statistical Analysis Plan
SCID	Structured Clinical Interview for DSM Disorders
SDMT	Symbol Digit Modalities Test
SNRI	selective serotonin and norepinephrine reuptake inhibitor
SOA	stimulus onset asynchrony
SPL	sound pressure level
SSRI	selective serotonin reuptake inhibitor
T3	triiodothyronine
T4	thyroxine
TBR	theta-beta ratio
TEAE	treatment-emergent adverse event
TESAE	treatment-emergent serious adverse event
T _{max}	time to reach maximum concentration
TSH	thyroid-stimulating hormone (
UDS	urine drug screen
ULN	upper limit of normal
WOCBP	woman of childbearing potential

